**Confidential**

**Definition:** Any diagnostic test or therapeutic procedure that was performed because of an ECG artifact or misdiagnosis made by clinician using monitoring technology

#### 4.2.3. Definition of Clinical and Qualitative Endpoints

1. RRT interventions

**Definition:** RRT's that are activated due to clinical deterioration as reported by the hospital or subject's medical record.

2. Survival rates post RRT interventions

**Definition:** Survival at discharge or study completion following RRT activation.

3. Code blue rates

**Definition:** Code blue teams that are initiated due to cardiopulmonary arrest as reported by the hospital or subject's medical record.

4. Unplanned intubations

**Definition:** An intubation and mechanical ventilation that was not planned during the course of the hospital stay.

5. Time of RRT activation to time of a threshold notification(s) from the SM system following clinical deterioration events

**Definition:** Time of RRT activation is the time that a clinician called or initiated the RRT team. Time of a threshold notification(s) is the time when the SM system alerts or alarms when a hospital protocol-defined threshold is exceeded.

6. Clinical team satisfaction with surveillance monitoring and study product

**Definition:** Clinical team (nurse or physician) who treated at least one study subject will be asked to take a qualitative survey on satisfaction and confidence.

7. Patient satisfaction with surveillance monitoring and study product

**Definition:** Each subject will be asked to take a qualitative survey on satisfaction and comfort at the end of enrollment.

8. Perceptions of clinicians who prescribe telemetry to patients without AHA indication

**Definition:** Each eligible clinician will be asked to take a qualitative survey focused on the AHA guidelines and the monitoring modalities of the study.

9. Clinicians' perceptions on telemetry utilization and impact on hospital resource utilization and patient flow

**Definition:** Each eligible clinician will be asked to take a qualitative survey focused on telemetry utilization and the monitoring modalities of the study.

## 5. Investigation Plan

This will be single-center, prospective, pilot, pre/post implementation study to collect post-market data on hospitalized subjects monitored via telemetry and surveillance monitoring.

This document is electronically controlled. Printed copies are considered uncontrolled.

**Confidential**

Subjects who meet all of the inclusion criteria and none of the exclusion criteria will be assigned to either one of the monitoring groups and then followed for the duration of their hospital stay.

[figure not shown]
The subject population will include up to a total of 280 subjects with up to 140 subjects in each monitoring group.

Each enrolled subject will be assigned to one of two types of monitoring arms: telemetry monitoring (TM) OR surveillance monitoring (SM) and then followed for the duration of their hospital stay up to 30 days ( $\pm$  2 days). The monitoring groups described in Section 10.1 of CIP will be enrolled in two prospective phases. The enrollment phase of the TM group will occur first. After TM subjects have completed study participation, the SM phase will initiate. Study flowchart is reported in Figure 1.

No randomization will be used during the course of the study. Assignment to a monitoring arm will be determined by the phase status of the study. During the TM phase, all subjects will be assigned to the TM group. During the SM phase, all subjects will be assigned to the SM group.

No blinding and interim analysis will occur during the course of the study.

**Figure 1. Study Flowchart.**

This document is electronically controlled. Printed copies are considered uncontrolled.

**Confidential**

---

## **6. Determination of Sample Size**

The study sample size is based on the primary non-inferiority objective of comparing hospital length of stay (LOS) between the surveillance monitoring (SM) and telemetry monitoring (TM) period on subjects without AHA telemetry indication. From similar study data published in the literature, we assume a similar LOS distribution for both monitoring groups with common coefficients of variation of 0.65. With a pre-specified non-inferiority margin of 0.2 for the mean ratio, a sample size of 132 in each group will provide more than 80% power to assess the objective at the significance level of 0.05. By taking into account potential attrition, a total of 140 subjects in each monitoring group will be used for this study.

---

## **7. Statistical Methods**

### **7.1. Study Subjects**

#### **7.1.1. Disposition of Subjects**

Subject disposition (e.g., number completing the study, number lost-to-follow-up) will be summarized with frequency tables.

#### **7.1.2. Clinical Investigation Plan (CIP) Deviations**

The investigator is required to conduct this study in accordance with the CIP, IRB requirements and applicable regulations.

A CIP deviation is defined as an event when the investigator or site personnel did not conduct the study according to the CIP or the clinical trial agreement. Thorough documentation of all deviations in source documents and transcription to eCRF is required, along with notification to your sponsor contact. Additionally, the site must complete the Deviation Log found in the ISF.

Major deviations are associated with subject safety or data integrity. They are defined as deviations with respect to:

- Patient informed consent procedure
- Patient eligibility criteria
- Study data collection and reporting

All deviations and reasons to deviate from the study protocol must be reported prior to deviation when planned or promptly after occurrence when unplanned to the sponsor regardless of whether medically justifiable, pre-approved by the sponsor, or taken to protect the subject in an emergency.

#### **7.1.3. Analysis Sets**

The primary effectiveness analysis will be based on all evaluable data from this study. A per protocol analysis will be performed based on all subjects who are compliant with the study protocol, i.e. who provide valid informed consents and do not experience any major protocol deviations.

The safety analysis will be based on all patients participated in the study.

This document is electronically controlled. Printed copies are considered uncontrolled.

**Confidential**

## 7.2. General Methodology

In general, descriptive statistics will be used to summarize baseline and study outcomes. For continuous variables, number of available observations, mean, standard deviation, median, minimum and maximum values will be provided. For categorical variables, frequency and percentage will be used. Unless otherwise specified, statistical assessments will be based on 2-sided tests at an alpha level of 0.05, which include Student-t or Wilcoxon rank-sum or ANOVA test for continuous variables, and Chi-square or Fisher's exact test for categorical variables. Multivariate regression models will be used to assess impacts of potential confounding variable. Statistical analysis will be performed using [REDACTED] (SAS Institute Inc., Cary, NC) or other valid statistical software.

The primary effectiveness analysis will be based on all evaluable data from this study. A per protocol analysis will be performed based on all subjects who are compliant with the study protocol, i.e. who provide valid informed consents and do not experience any major protocol deviations.

For safety assessments, adverse events (AEs) will be summarized using frequency counts and percentages. Descriptive statistics will be provided by monitoring group and by severity and relationship. Additionally, differences between the two monitoring groups will be summarized along with 95% confidence intervals. Individual listings of adverse events, including event type, start date, duration, severity, and device-relatedness will be provided as appropriate. The safety analysis will be based on all patients participated in the study.

Further, a health economic analysis will be performed based on healthcare economic and resource utilization data collected in this study. Monitoring effectiveness, QoL in the form of Quality-Adjusted Life-Years (QALYs), life-years gained and other data collected in this study may be used as inputs to the model.

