### 10.2.3. End of Study Visit

The last visit will be on the day the subject is discharged from the hospital or at day 30 ( $\pm$  2 days) of hospital admission. Subject participation ends at this visit or if the subject is withdrawn from the study for any reason. The following procedures and assessments will be performed **during both phases of the study** at the end of the study and will be recorded on the subject eCRFs.

- Check and record AEs/SAEs and protocol deviations
- Collect the following from the medical and billing records (UB04):
  - Hospital History data
  - Healthcare Economic data
  - Resource Utilization data
- Verify data and enter into eCRF within 5 preferred business days of collection

**During the SM Phase only**, the following procedures and assessments will be performed.

- Remove BioModule, BioModule holder and electrodes. Discard disposable BioModule holder and electrodes.
- Clean reusable BioModule and return to the charging station
- Assess for and document any device deficiencies
- Subject complete Patient Satisfaction Questionnaire
- Eligible clinicians complete Clinical Team Satisfaction Questionnaire
- Eligible clinicians complete Telemetry Utilization Questionnaire for Clinicians (POST)
- Eligible clinicians complete Perception Questionnaire for Prescribing Clinicians (POST)

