##### 4.1.2. Secondary Healthcare Economic and Resource Utilization Objectives

1. Compare telemetry bed, emergency department (ED) bed, and intensive care unit (ICU) bed availability between monitoring periods
2. Compare associated health care costs between monitoring periods
3. Compare the number of ICU, ED, PACU, and telemetry delays in transfer between monitoring periods
4. Compare the number of hospital unit transfers between monitoring groups
5. Compare the number of unplanned ICU transfers between monitoring groups
6. Compare ICU LOS for subjects having unplanned transfers to the ICU between monitoring groups
7. Compare the number of unnecessary diagnostic tests and therapeutic procedures generated by artifacts and/or misdiagnosis between monitoring groups

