### 4.2.2. Definition of Secondary Healthcare Economic and Resource Utilization Endpoints

1. Telemetry bed, ED, and ICU bed availability

**Definition:** Daily available number of beds available in both telemetry ED, and the ICU measured daily in hours from 12:00 AM to 11:59 PM.

2. Associated health care costs

**Definition:** Costs attributable to the primary and secondary clinical and resource utilization endpoints.

3. ICU, ED, PACU, and telemetry delays in transfer

**Definition:** Number of patients delayed admission to the ICU, ED, PACU, and to a telemetry bed.

4. Hospital unit transfers

**Definition:** Number of inpatient transfers from one unit to another unit during course of hospital stay.

5. Unplanned ICU transfers

**Definition:** Direct transfers from either study monitoring group to the ICU where the transfer was not planned during the hospital stay. For example, a transfer may be planned in advance of certain procedures for high risk patient as a preventative measure. The study team will determine if transfer were considered planned versus unplanned by review of the medical record.

6. LOS for ICU transfers

**Definition:** The LOS (time in minutes) in the ICU for subjects who have an unplanned transfer to the ICU.

7. Diagnostic tests and therapeutic procedures generated by artifacts and/or misdiagnosis

This document is electronically controlled. Printed copies are considered uncontrolled.

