## 7.9. Evaluation of Objectives

The primary study endpoint is hospital of length of study (LOS), which is calculated from date of admission and discharge. The primary objective is to demonstrate that LOS of the SM group is similar (non-inferior) to the TM group.

Additionally, if the non-inferiority objective is met, superiority will also be assessed (without statistical penalty) to further understand the effectiveness of SM versus TM. The corresponding superiority hypothesis becomes: [REDACTED] (i.e., SM has shorter LOS duration than TM).

Secondary clinical and qualitative endpoints include:

- number of RRT interventions between monitoring groups
- survival rates post RRT interventions between monitoring groups
- Time of RRT activation to time of threshold notifications from SM system following clinical deterioration events
- code blue rates between monitoring groups
- unplanned intubations between monitoring groups
- clinical team satisfaction with surveillance monitoring and study product
- patient satisfaction with surveillance monitoring and study product
- perceptions of clinicians who prescribe telemetry to patients without AHA indication
- Clinicians' perceptions on telemetry utilization and impact on hospital resource utilization and patient flow

Additionally, healthcare economic and resource utilization data will be collected to evaluate:

- telemetry bed, ED, and ICU bed availability between monitoring periods
- associated health care costs between monitoring periods

This document is electronically controlled. Printed copies are considered uncontrolled.

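### The SAP names no summary measure or test for the secondary cost objective, and one of the default tests it allows does not compare mean cost

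*SAP*

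**What the plan says.** SAP 4.1.2 lists as its second economic objective "Compare associated health care costs between monitoring periods". SAP 4.2.2 defines the endpoint as "Costs attributable to the primary and secondary clinical and resource utilization endpoints". It names no mean, median or total, and no unit of analysis.

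SAP 7.9 repeats the item ("associated health care costs between monitoring periods") in a list, with no test or summary measure attached. SAP 7.11, Health Outcomes Analyses, reads N/A.

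The only tests that can apply are the defaults in SAP 7.2, repeated in Protocol 13.3. They hold wherever no other method is given, and are two-sided at the 0.05 level. The menu is worded "which include Student-t or Wilcoxon rank-sum or ANOVA test for continuous variables". Nothing says when each is used. The Statistics row of the protocol synopsis is narrower and gives only one-way ANOVA for continuous variables.

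SAP 7.2 also promises means and standard deviations, regression for potential confounders, and that "a health economic analysis will be performed based on healthcare economic and resource utilization data collected in this study". It gives that economic analysis no method. Under Protocol 10.2.3, economic data are taken from medical and billing records at each subject's end-of-study visit.

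**The concern.** The tests on the menu answer different questions. The t-test and ANOVA compare mean cost, and mean cost times the number of patients is total cost. Wilcoxon compares ranks: an ICU stay counts as one high rank, however expensive it was.

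Cost data are usually right-skewed, and skewness is a common reason to prefer a rank test. The SAP leaves that choice open until the data have been seen. Suppose SM makes the typical stay cheaper and also adds a few very costly stays. The rank test then responds mainly to the first effect and gives little weight to the second. The study could report lower cost under SM when the mean is the same or higher.

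The plan treats both components as open questions. Protocol 5.1 expects less telemetry to shorten stay and reduce cost, and unplanned ICU transfers and ICU length of stay (LOS) are comparative secondary endpoints.

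**Working it through.** **The plan's own figure.** The documents give no figure for cost. The only related one is the LOS sample size (SAP 6, Protocol 13.1): 132 per group, coefficient of variation (CV) 0.65, margin 0.2 on the mean ratio, power above 80%, level 0.05. On the log scale:

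- variance = ln(1 + 0.65²) = ln 1.4225 = 0.3524
- n = 2 × 0.3524 × (1.645 + 0.842)² / (ln 1.2)² = 131.1, so 132 per group

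This reproduces with one-sided 0.05. I borrow the CV and the group size for cost.

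**Inputs for cost**

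- From the documents: two-sided 0.05; 132 per group; up to 220 per group (Protocol 13.1). SAP 6 says 140, which disagrees with the protocol but lies close to 132.
- Borrowed: CV 0.65, which is the documents' figure for LOS and not for cost.
- Assumed: lognormal ward cost with mean 10 units in the telemetry (TM) group; an added ICU cost of 30 units (3 times mean ward cost); a 3% ICU share in TM.

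**Setting equal means.** TM mean = 10 + 0.03 × 30 = 10.9. For a ward-cost cut c under SM, the SM ICU share p solves 10(1 − c) + 30p = 10.9:

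- c = 5%: p = 1.4/30 = 4.7%
- c = 10%: p = 1.9/30 = 6.3%
- c = 15%: p = 2.4/30 = 8.0%

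**Simulated share of trials declaring SM cheaper, true means equal (nominal 2.5%)**

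| Ward-cost cut | Wilcoxon, 132 per group | Wilcoxon, 220 per group | t-test |
|---|---|---|---|
| None, identical distributions | 2.4-2.8% | 2.4-2.8% | about 2-3% |
| 5% | about 6% | about 7% | about 2-3% |
| 10% | about 12% | about 20% | about 2-3% |
| 15% | about 24% | about 35% | about 2-3% |

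Repeat runs moved the Wilcoxon figures by up to about two percentage points.

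**SM truly dearer.** With the 15% cut and a 9% ICU share, SM mean = 8.5 + 2.7 = 11.2 against 10.9. Wilcoxon still declares SM cheaper in about 18-20% of trials at 132 and 28% at 220; the t-test does so in 1-2%.

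**Other assumptions.** A second set used a 2% TM ICU share, ICU cost 4 or 8 times ward cost with CV 1, and SM ward cost 0.80-0.90 of TM. At equal means Wilcoxon favoured SM in 17-68% of trials at 132 and 25-88% at 220. With SM about 9% dearer the figures were 10-60% and 13-82%. The t-test rejected in either direction in 4.5-5.8% at equal means and 132 per group. Its errors were not evenly split: in the steepest case about 5% fell on the side favouring SM.

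**The case against.** The strongest reply is that nothing assigns Wilcoxon to cost. Two of the three tests in SAP 7.2 compare means, the synopsis names only ANOVA, means will be reported beside any test, and a separate health economic analysis is promised. All of this is correct. It means the plan may end up with a mean comparison, and a reader could notice a rank test and a pair of means that disagree. It does not say which result would be the study's answer on cost.

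Three stronger readings are tempting, and the documents do not support them.

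- A reader might infer that rare ICU stays drive total cost in this population. The documents give no ICU rate, ICU cost or cost distribution. Rare ICU stays alone also do no harm: with the same distribution in both groups Wilcoxon keeps its level. The reversal needs cheaper typical stays and more (or costlier) ICU stays under SM together.
- A reader might infer that SM is expected to raise ICU use. Protocol 5.1 points the other way: it cites a 70% cut in telemetry with no change in code blue, mortality or rapid response rates.
- A reader might infer that ICU days will be counted twice, because the endpoint is defined through endpoints that overlap. That is one possible reading of the definition in SAP 4.2.2, but the text does not say that endpoint costs are added up.

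The size also depends on the ward-cost cut. At 5%, the error is about 6-7%, not a quarter of trials or more. Finally, this is one of several secondary objectives in a single-center pilot.

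**Conclusion.** The concern holds as a gap in specification. The cost objective has no summary measure and no test of its own, the default menu has no rule for choosing, the synopsis and SAP 7.2 differ, and the announced economic analysis has no method. One permitted option, Wilcoxon, can point the wrong way for mean cost.

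Under the main assumptions and equal means, it favours SM in about 6-24% of trials at 132 per group and 7-35% at 220, against a nominal 2.5%. These figures rest on a CV borrowed from LOS, an assumed ICU share and cost, and opposite effects on ward cost and ICU use. They show what the open choice permits, not what this study will find. The gap should be closed before the cost data are analysed, but it does not affect the primary analysis.

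**What to change.** In SAP 7.2 and 7.9, state that cost is compared as the difference (or ratio) in arithmetic mean total index-admission cost per subject, with a bootstrap 95% interval or a gamma log-link model using the baseline covariates. State that any rank test of cost is descriptive only. Bring the protocol synopsis into line, and either give the health economic analysis in SAP 7.2 a method, and reconcile it with the N/A in 7.11, or remove it.

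Take each subject's admission total from the billing record once, and show endpoint-level costs only as a breakdown. This also removes any doubt about overlapping costs.

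The cost is SAP wording and standard procedures; the billing data are already collected per subject. The downside is a wider interval than a rank test would suggest. With few, very costly stays even a mean-based interval may have uneven tails, so the cost result should be read with its interval and not as a bare p-value.

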**13. Statistical Design and Methods**

**13.1. Sample Size Justification**

The study sample size is based on the primary non-inferiority objective of comparing hospital length of stay (LOS) between the surveillance monitoring (SM) and telemetry monitoring (TM) period on subjects without AHA telemetry indication. From similar study data published in the literature, we assume a similar LOS distribution for both monitoring groups with a common coefficients of variation of 0.65. With a pre-specified non-inferiority margin of 0.2 for the mean ratio, a sample size of 132 in each group will provide more than 80% power to assess the objective at the significance level of 0.05. Assuming at least 30% attrition from withdrawals and screen failures, up to 220 recruited subjects in each monitoring group will be used for this study.

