### 7.10. Safety Evaluation

Only the following adverse events will be collected for this study:

- Any adverse events noting mild or moderate physiological deterioration
- Any adverse event whose relationship to the study device is: possible, probable, definite, or unknown/ impossible to determine, regardless of what the event may be.
- All SAEs, of any relationship, meeting definition in section 12.2 of the CIP must be reported.

The recording of adverse events for all enrolled subjects begin after the study devices are attached and ends with the subject's completes study enrollment. Completion is defined by when a subject is discharged from the hospital, completes 30 day ( $\pm$  2 days) enrollment period, or if the subject is withdrawn from the study for any reason.

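### The AE comparison uses percentages over unequal observation windows, so it also reflects days observed; a per-patient-day rate should be added beside it

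*SAP*

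**What the plan says.** SAP 7.2 gives the AE summary measure: "For safety assessments, adverse events (AEs) will be summarized using frequency counts and percentages". For the comparison, "differences between the two monitoring groups will be summarized along with 95% confidence intervals". SAP 7.1.3 sets the population: "The safety analysis will be based on all patients participated in the study". The SAP does not say whether a percentage is of subjects or of events; subjects is the natural reading.

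SAP 7.10, like Protocol 12, sets the observation window. It opens as follows: "The recording of adverse events for all enrolled subjects begin after the study devices are attached". It closes at the first of three events: "Completion is defined by when a subject is discharged from the hospital, completes 30 day" (plus or minus 2 days), "or if the subject is withdrawn from the study for any reason". Protocol 7.1 rules out follow-up after discharge. For withdrawn subjects, SAP 7.4 provides only for final outcomes data from the medical record.

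Neither document defines patient-days, an exposure-adjusted AE rate, a time-to-first-AE analysis or a common AE window. The regression modelling in SAP 7.2 is aimed at confounders in general and is not tied to AEs or to days observed.

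**The concern.** A percentage of subjects compares two groups fairly when both are watched for about the same time. Here the window is largely the subject's own hospital stay, and length of stay is what the study sets out to compare. SAP 6 sets a non-inferiority margin of 0.2 on the mean ratio, naturally read as SM/TM up to 1.2, and SAP 7.9 goes on to test whether stays are shorter under surveillance monitoring (SM) than under telemetry monitoring (TM). If SM shortens stay, SM subjects are observed for less time and, at the same daily risk, show fewer AEs. If SM lengthens stay, the reverse holds.

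Withdrawal acts in the same way. Protocol 10.10 lists technical failure of data collection from the Vital Sync system as a reason to withdraw, and this can arise only under SM. A subject withdrawn on day 1 counts as much in the denominator as one observed for ten days.

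What is at stake is how the safety table is read. Part of any AE difference could repeat the length-of-stay or withdrawal result and say nothing separate about risk while monitored. The design is sequential, unblinded and not randomised, and has no data monitoring committee, so this table carries much of the between-group safety evidence.

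**Working it through.** **Inputs from the documents.** CV of stay 0.65; margin 0.2 on the mean ratio; 132 per group evaluable (SAP 6); 140 per group enrolled (SAP 5 and 6) or up to 220 (Protocol 13.1); 30-day cap.

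**Assumed, because the documents are silent.** Mean stay 4 days; AE risk 3% per day, constant and equal in both groups; lognormal stay.

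**Step 1: the plan's own figure.** Log-scale SD = √ln(1 + 0.65²) = 0.594. With margin ln 1.2 = 0.1823, one-sided alpha 0.05 and 80% power, n = 2 × 0.594² × (1.645 + 0.842)² / 0.1823² ≈ 131.1, so 132 per group. The stated size reproduces. This supports reading the margin as a ratio of 1.2 and using a lognormal stay with CV 0.65. The plan states no AE rate or AE precision to reproduce.

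**Step 2: effect of stay.** The AE percentage is the average of 1 − exp(−0.03 t) over the distribution of stay t, capped at 30 days.

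| Mean-stay ratio | Mean stay (days) | Subjects with an AE | Relative change | First AEs per 100 days at risk |
|---|---|---|---|---|
| 0.8 | 3.2 | 8.98% | −19% | 3.0 |
| 1.0 | 4.0 | 11.05% | – | 3.0 |
| 1.2 | 4.8 | 13.05% | +18% | 3.0 |

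The absolute shift is about 2 points either way. With AE percentages from 2% to 30% and mean stays from 3 to 7 days, ratios of 0.8 and 1.2 give relative changes of 15-20%, or about 0.4 to 4.9 points.

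**Step 3: effect of withdrawal.** A share w of one group is cut at a uniformly distributed point of its stay. A subject so cut has an AE recorded with probability 1 − (1 − e^(−ht))/(ht), where h = 0.03; this averages 5.68%. The group percentage is (1 − w) × 11.05% + w × 5.68%.

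- w = 10%: 10.5% (−5% relative)
- w = 20%: 10.0% (−10%)
- w = 30%: 9.4% (−15%)

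With 30% withdrawn under SM and 10% under TM, the ratio is 9.44/10.51 = 0.90, a gap of 1.1 points at equal daily risk.

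**Step 4: if AEs cluster early.** With a front-loaded hazard (Weibull, shape 0.5) set to give the same 11.05%, stay ratios of 0.8 and 1.2 give 9.95% and 12.03%, changes of −10% and +9%. The stay effect roughly halves.

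**Step 5: against the planned precision.** The half-width for 11.05% against 8.98% at 140 per group is 1.96 × √[(0.1105 × 0.8895 + 0.0898 × 0.9102)/140] = 7.0 points. Against 13.05% it is 7.6. At 220 per group the two figures are 5.6 and 6.1.

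**The case against.** Several points on the other side stand.

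- The AE output is descriptive. The plan has no safety hypothesis or test, and percentage per admission is a legitimate measure of in-hospital burden. If SM shortens stay, fewer in-hospital AEs is part of what the strategy does. Per admission or per day is partly a choice of estimand.
- The sample-size sections assume similar stay distributions in the two groups; if that holds, the stay route disappears. The margin limits longer SM stays only, so the ratio of 0.8 is a scenario for the superiority case, not something the plan specifies.
- The protocol's attrition assumption reads: "Assuming at least 30% attrition from withdrawals and screen failures". Under Protocol 9.2, screen failures exit at once, and they include subjects who never start monitoring. Treating all 30% as withdrawals is therefore an upper-end scenario. No document supports a 30% against 10% split.
- The artefact is several times smaller than the interval half-width in the worked case.

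The last point limits the consequence but does not remove the bias: a wide interval is still centred in the wrong place if the target is daily risk. The others narrow the claim without meeting it, because nothing in the plan lets a reader separate days observed from risk per day.

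Two stronger readings are tempting. One is that the group difference itself can move by 10-20%, or by 10-20 points. At equal daily risk the true difference is zero, so a percentage of it has no meaning; what changes is one group's percentage, in relative terms and conditionally. The other is that the percentages are invalid and a rate should replace them as the sole basis for safety. The documents do not support that either, since the percentages answer a reasonable question and the rate has weaknesses of its own.

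**Conclusion.** The point holds as a conditional one. The planned AE contrast mixes risk with days observed, and days observed may differ because they follow the primary endpoint and a withdrawal pattern that may differ by group. If mean stay differs by 20% at equal constant daily risk, one group's AE percentage shifts by about 18-19% relative, or about 2 points. Withdrawals of 10%, 20% or 30% in one group lower its percentage by about 5%, 10% or 15% relative. These sizes rest on the assumed 4-day mean stay, 3% daily risk and uniform withdrawal time; none is a document figure. The stay effect roughly halves with early clustering, and the shifts lie within the planned interval width. This calls for a cheap improvement to the SAP. A reader might infer that SM is bound to look safer than it is; the documents do not show that, because they give no expected stay difference or withdrawal rate by group.

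**What to change.** In SAP 7.2 and 7.10:

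1. Keep the percentages and state their denominator as subjects in whom the assigned monitoring started.
2. Add, by group, total observed patient-days and AEs and SAEs per 100 observed patient-days. Give the SM/TM rate ratio with a 95% CI from a Poisson or negative binomial model with log observed days as offset and robust variance. Read it alongside the percentage difference.
3. Define the start of AE person-time in TM. Recording is tied to attachment of study devices, and Protocol Table 1 places the BioModule in the SM phase only. Start of the assigned monitoring in both groups is one option. Confirm that this date and time are captured, since Protocol 10.2.1 and Table 1 do not list them.
4. Reconcile the origin of the 30-day limit, which is enrolment in Protocol 7.1 but hospital admission in Protocol 10.2.3, because it fixes the end of person-time.
5. Report withdrawals by reason and group.

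The cost is a few lines of SAP text, one table, and possibly one added data field. AE onset dates and study completion dates are already provided for. State the limits: the rate assumes roughly constant risk over the stay; it does not correct for withdrawal prompted by clinical change, such as newly prescribed continuous monitoring; and it is diluted when an AE itself prolongs the stay.
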